8. On a stable diet and exercise regime at screening with no intention to modify diet or exercise pattern during the trial, ie, no weight reduction program intended during the trial or within the last 90 days prior to or through screening.
9. No plans to undergo bariatric surgery during the trial.
10. Fundoscopy at screening without signs/symptoms of intracranial hypertension or diabetic retinopathy stage 2 / moderate or above or any other retinal disease contraindicated to growth hormone therapy. For subjects with a diagnosis of diabetes mellitus at screening, this must be documented with a fundus photograph.
11. Able and willing to provide a written Informed Consent Form (ICF) and authorization for protected health information (PHI) disclosure in accordance with Good Clinical Practice (GCP).
12. Serum ft4 in the normal range at screening as measured by central laboratory.

Exclusion Criteria

1. Known Prader-Willi Syndrome and/or other genetic diseases that may have an impact on an endpoint.
2. Diabetes mellitus at screening if any of the following criteria are met:
 - a. Poorly controlled diabetes, defined as $\text{HbA}_{1c} > 7.5\%$ at screening according to central laboratory
 - b. Diabetes mellitus (defined as $\text{HbA}_{1c} \geq 6.5\%$ and/or fasting plasma glucose $\geq 126 \text{ mg/dL}$ and/or plasma glucose $\geq 200 \text{ mg/dL}$ two hours after oral glucose tolerance test) diagnosed < 26 weeks prior to screening
 - c. Change in diabetes regimen (includes dose adjustment) within < 90 days prior and throughout screening
 - d. Use of any diabetes drugs other than metformin and/or DPP-4 inhibitors for a cumulative duration of greater than 4 weeks within 12 months prior to screening
 - e. Diabetes-related complications at screening (ie, nephropathy as judged by the investigator, neuropathy requiring pharmacological treatment, retinopathy stage 2 / moderate and above within 90 days prior to screening or during screening)
3. Active malignant disease or history of malignancy. Exceptions to this exclusion criterion:
 - a. Resection of in situ carcinoma of the cervix uteri
 - b. Complete eradication of squamous cell or basal cell carcinoma of the skin
 - c. Subjects with GHD attributed to treatment of intracranial malignant tumors or leukemia, provided that a recurrence-free survival period of at least 5 years prior to screening is

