5. For subjects on hormone replacement therapies for any hormone deficiencies other than GH (eg, adrenal, thyroid, estrogen, testosterone) must be on adequate and stable doses for ≥ 6 weeks prior to and throughout screening.

Note: Short-term increases in glucocorticoid doses taken on an as-needed basis for adrenal insufficiency are permitted (“stress dose” allowance: duration up to 5 days up to 2 times in 6 weeks, the maximum dose may reach 3 times the stable dose). One-time dose increases for diagnostic or other medical procedures are allowed.

Note: For subjects receiving oral estrogen or estrogen-containing therapy, subjects must intend to maintain the same dose and route of estrogen administration throughout the trial. For subjects receiving non-oral estrogen or estrogen-containing therapy, the dose may be adjusted as required, however subjects must intend to maintain the same route of administration throughout the trial.

6. For subjects not on glucocorticoid replacement therapy, documentation of adequate adrenal function at screening defined as: morning (6:00-10:00AM) serum cortisol $>15.0 \mu\text{g/dL}$ (measured at central laboratory) and/or Adrenocorticotrophic Hormone (ACTH) stimulation test or ITT with serum cortisol $>18.0 \mu\text{g/dL}$ at or within 90 days prior to screening. Stimulation test protocols and results are subject to review and approval by the Medical Monitor.
7. For males not on testosterone replacement therapy: morning (6:00-10:00AM) total testosterone within normal limits for age as measured by the central laboratory at screening.
8. On a stable diet and exercise regime at screening with no intention to modify diet or exercise pattern during the trial, ie, no weight reduction program intended during the trial or within the last 90 days prior to or through screening.
9. No plans to undergo bariatric surgery during the trial.
10. Fundoscopy at screening without signs/symptoms of intracranial hypertension or diabetic retinopathy stage 2 / moderate or above or any other retinal disease contraindicated to growth hormone therapy. For subjects with a diagnosis of diabetes mellitus at screening, this must be documented with a fundus photograph.

11. Able and willing to provide a written ICF and authorization for protected health information (PHI) disclosure in accordance with Good Clinical Practice (GCP).
12. Serum fT4 in the normal range at screening as measured by central laboratory.

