
7. Subjects with prior cranial irradiation or hypothalamic-pituitary surgery: the procedure took place less than 12 months prior to screening.
8. eGFR <60 mL/min/1.73m² determined based on Modification of Diet in Renal Disease (MDRD) equation using serum creatinine from the central laboratory at screening.
9. Hepatic transaminases (ie, AST or ALT) >3 times the upper limit of normal according to the central laboratory at screening.
10. Heart failure NYHA class 3 or greater ([NYHA 1994](#)).
11. QTcF \geq 451 milliseconds on 12-lead ECG at screening.

Note: If the initial measurement is out of range, the assessment should be repeated 2 more times and the average QTcF value should be used to determine the subject's eligibility.

12. Poorly controlled hypertension, defined as supine systolic blood pressure >159 mmHg and/or supine diastolic blood pressure >95 mmHg at screening

Note: if the initial measurement is out of range, may be repeated 2 more times after 15 min and exclusion will be based on the average of the three measurements.

13. Cerebrovascular accident within 5 years prior to screening.
14. Anabolic steroids (other than gonadal steroid replacement therapy) or oral/intravenous/intramuscular corticosteroids (other than in replacement or stress doses as described in Inclusion Criterion No.5) within 90 days prior to or throughout screening.

Note: Stable doses of inhaled, intra-articular, or topical corticosteroids are permitted.

15. Currently using or have used within 26 weeks prior to screening any weight-loss or appetite-suppressive medications including orlistat, zonisamide, lorcaserin, bupropion, topiramate, sibutramine, stimulants (eg, phentermine or ADHD medications such as methylphenidate or amphetamines), GLP-1 receptor agonists (eg, dulaglutide, exenatide, liraglutide, lixisenatide, semaglutide), SGLT-2 inhibitors (eg, canagliflozin, dapagliflozin, empagliflozin, sotagliflozin) or medications that affects IGF-1 or GH measurements including cabergoline at doses above 0.5 mg weekly or bromocriptine at doses above 20 mg weekly.

Note: if it can be documented that no weight-loss occurred with these drugs, a 90-day withdrawal period prior to screening is sufficient.

16. Known history of hypersensitivity and/or idiosyncrasy to any of the test compounds (somatropin) or excipients employed in this trial.
17. Known history of neutralizing anti-hGH antibodies.
18. Inability to undergo scanning by DXA or a non-interpretable DXA scan at screening.

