19. Female who is pregnant, breast-feeding or intends to become pregnant or is of childbearing potential (i.e., fertile, following menarche and until becoming post-menopausal unless permanently sterile) and not using adequate contraceptive methods

- Acceptable highly effective methods of contraception include intrauterine device (IUD); intrauterine system (IUS); bilateral tubal occlusion (must be documented); combined or progestogen-only hormonal contraception associated with inhibition of ovulation; vasectomized partner (must be documented); or sexual abstinence (only when it is the usual and preferred lifestyle of the subject).
- Clinically acceptable methods of birth control include male or female condom with or without spermicide; progestogen-only oral hormonal contraception, where inhibition of ovulation is not the primary mode of action; or cap, diaphragm, or sponge with spermicide.
- Permanent sterilization includes hysterectomy, bilateral salpingectomy, and bilateral oophorectomy.

Note: Females of childbearing potential must accept to use the above-mentioned methods of contraception from the beginning of screening to the last trial visit.

Note: Periodic abstinence (e.g., calendar, ovulation, symptothermal, post-ovulation methods) and withdrawal are not acceptable methods of contraception.

Note: For subjects using oral combined hormonal contraception (ie containing estrogen), the dose and route must be stable for ≥ 6 weeks prior to screening and throughout the trial

20. Male subjects must use a condom, or his female partner of childbearing potential must use an effective form of contraception as described above, from the beginning of screening to the last trial visit.

21. Known substance abuse or known (or previous) eating disorders, including anorexia nervosa, bulimia and severe gastrointestinal disease affecting normal eating (as judged by the investigator).

22. Any disease or condition that, in the judgement of the investigator, may make the subject unlikely to comply with the requirements of the trial or any condition that presents undue risk from the investigational product or procedures.

23. Participation in another interventional clinical trial involving an investigational compound within 26 weeks prior to screening or in parallel to this trial.

24. Currently using or have used within the last 3 days prior to screening: biotin >0.03 mg/day from supplements

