10.4. PER-PROTOCOL ANALYSIS SET

The Per-Protocol Analysis Set will be a subset of Intent to Treatment population. This set will exclude subjects with the following protocol deviation during the trial:

- Treatment Non-Compliance (Missed or overdosed) at least +/- 20 % of lonapegsomatropin, placebo, or daily somatropin doses during the treatment period
- Failed to have a DXA measurement at Week 38 visit
- Violates major inclusion or exclusion criteria (inclusion 02,03,04 or exclusion 07,15,18)
- Early termination defined as subjects who withdraw from the trial prior to Week 38 visit

- Any Prohibited therapies and procedures:
 - anti-obesity drugs/appetite suppressants (unless prescribed for indication other than weight loss/obesity)
 - GLP-1 receptor agonists (even if indicated for diabetes mellitus)
 - hGH therapies other than trial drug, GH secretagogues
 - bariatric surgery
 - anabolic steroids other than testosterone
 - cabergoline >0.5 mg/week or bromocriptine >20 mg/week (due to their effects on lowering IGF-1 and GH hormonal concentrations and their independent effects on weight)

The Per-Protocol analysis set will be used for sensitivity analysis of the primary efficacy endpoint. The Per-Protocol analysis set and the criteria will be identified prior to unblinding the trial.

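### The Per-Protocol set in SAP 10.4 does not remove violators of Exclusion 01 or Inclusion 08, or subjects on weight-reducing programs or diets during the trial

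*Protocol*

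**What the plan says.** SAP 10.4 defines the Per-Protocol set as the ITT population minus subjects with certain deviations. The third bullet covers eligibility: "Violates major inclusion or exclusion criteria (inclusion 02,03,04 or exclusion 07,15,18". The bracket closes there, with nothing to suggest that the six are examples.

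Two of the listed criteria concern the endpoint directly. Exclusion 15 begins "Currently using or have used within 26 weeks prior to screening any weight-loss or appetite-suppressive medications", and Exclusion 18 reads "Inability to undergo scanning by DXA or a non-interpretable DXA scan at screening".

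Two unlisted criteria also concern it:

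- Exclusion 01 (Protocol 8.1.2 and Synopsis): "Known Prader-Willi Syndrome and/or other genetic diseases that may have an impact on an endpoint".
- Inclusion 08 (Protocol 8.1.1 and Synopsis): "On a stable diet and exercise regime at screening with no intention to modify diet or exercise pattern during the trial", explained as "no weight reduction program intended during the trial or within the last 90 days prior to or through screening".

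The last group of bullets in SAP 10.4 covers therapies used on study: anti-obesity drugs and appetite suppressants, GLP-1 receptor agonists, other growth hormone products and secretagogues, bariatric surgery, anabolic steroids other than testosterone, and higher-dose cabergoline or bromocriptine. Protocol 9.9.2.2 also prohibits weight-reducing programs and diets, except diets indicated for diabetes. The SAP bullets do not carry that item over.

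The Per-Protocol set is used for Sensitivity Analysis 1 of the primary endpoint (SAP 12.10.4). SAP 10.4 says that the set and its criteria will be settled before unblinding.

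**The concern.** A per-protocol analysis of a body-composition endpoint should leave out subjects whose body fat may be changing for reasons the protocol tried to screen out. Exclusion 01 is the criterion that the protocol itself justifies by its effect on an endpoint. Inclusion 08 is the behavioural counterpart of Exclusion 15: one keeps out weight loss by drug, the other weight loss by diet, exercise or program. The SAP removes violators of one and keeps violators of the other.

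What is at stake is how Sensitivity Analysis 1 reads. It is the only one of the four sensitivity analyses that is restricted to subjects who followed the protocol; Sensitivity Analysis 2 is a completer analysis. If it keeps subjects on a weight-reduction program, its agreement or disagreement with the ITT result is a little harder to interpret.

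**Working it through.** **Step 1. Set the routes to non-drug change side by side.** Inputs: Protocol 8.1.1, 8.1.2 and 9.9.2.2; SAP 10.4.

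| Route | At entry | During the trial |
|---|---|---|
| Weight-loss drugs | Exclusion 15: on the list | Removed by a prohibited-therapy bullet |
| Bariatric surgery | Inclusion 09 (none planned): not on the list | Removed by a prohibited-therapy bullet |
| Weight-reduction program or diet | Inclusion 08: not on the list | Prohibited by the protocol; no SAP bullet |
| Genetic disease affecting an endpoint | Exclusion 01: not on the list | Not applicable |

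Of the three weight-loss routes, only the program or diet route is open at both ends. Planned surgery is caught if it takes place.

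**Step 2. Check the remaining exits.** The other bullets in SAP 10.4 are dose non-compliance of 20% or more, no Week 38 DXA, and early termination. None depends on diet or genetic disease. A subject in either group who takes the doses and attends Week 38 stays in the set.

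**Step 3. Reproduce the design figure.** Inputs from Protocol 14.2: n = 80 per arm, difference 1.9, SD 3.7, two-sided 5%. Power = Φ(δ / (σ√(2/n)) − 1.96). The standard error is 3.7 × √(2/80) = 0.585, and 1.9 / 0.585 = 3.248. Then Φ(3.248 − 1.96) = Φ(1.288) = 90.1%. The noncentral t with 158 df gives 89.8%. The stated 90% reproduces, and nothing in this point changes it.

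**Step 4. Size of a chance imbalance (assumed inputs).** The documents give no violator rate. If one arm has a net excess of k retained subjects, each shifted by s points for non-drug reasons, the difference moves by k × s / n. With n = 80:

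- k = 1, s = 3: 3/80 = 0.04, or 2% of 1.9
- k = 2, s = 5: 10/80 = 0.125, or 7%
- k = 4, s = 10: 40/80 = 0.50, or 26%

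With an assumed Per-Protocol arm of 70, k = 1 and s = 10 gives 10/70 = 0.14; k = 3 and s = 10 gives 30/70 = 0.43. A 10-point shift is 10/3.7 = 2.7 planned SDs, so the upper figures are extreme. Even 0.50 is below one standard error of the difference (0.585).

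**Step 5. Size of a balanced dilution (assumed inputs).** Let a fraction f of each arm be such subjects with no treatment effect, with SD still 3.7. If kept, the difference is 1.9(1 − f) at n = 80. If removed, it is 1.9 at n = 80(1 − f).

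| f | Difference if kept | Power if kept | Power if removed |
|---|---|---|---|
| 1% | 1.88 | 89.5% | 89.8% |
| 2% | 1.86 | 88.9% | 89.5% |
| 5% | 1.81 | 87.0% | 88.6% |
| 10% | 1.71 | 83.2% | 86.9% |

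At the low rates that pre-randomization eligibility review should produce, keeping or removing these subjects changes power by less than one percentage point.

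**The case against.** The strongest case on the other side is that this is a drafting preference with little effect. The Per-Protocol set serves one sensitivity analysis out of four. The primary analysis is ITT under a treatment-policy strategy (SAP 12.10.1). The Medical Monitor reviews all results before randomization (Protocol 10.2.1), so violators should be few. Entry violations precede randomization, so their expected imbalance between arms is zero. All of this stands, and it is why the point is minor. Two limits apply. Exclusion 01 rests on a known diagnosis and Inclusion 08 on reported habits and intentions, so review of results is less able to catch them than a laboratory value or a scan. Programs started on study begin after randomization, so the zero-expectation argument does not cover them automatically, although the weekly arms are blinded.

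A second objection is that any extension must stop somewhere. Exclusion 14 ("Anabolic steroids (other than gonadal steroid replacement therapy) or oral/intravenous/intramuscular corticosteroids") and Exclusion 21 ("Known substance abuse or known (or previous) eating disorders, including anorexia nervosa, bulimia") also bear on body composition and are unlisted. That is fair: these are judgement calls. Exclusion 01 and Inclusion 08 have the clearest claim, because the protocol ties the first to an endpoint and the second is the counterpart of a listed criterion.

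A reader might infer more than the documents support:

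- **That SAP 10.4 ignores the criteria protecting body fat.** It does not: Exclusions 15 and 18 are listed, and several on-study confounders have their own bullets.
- **That Exclusion 07 (recent surgery or irradiation) is a poor choice.** Protocol 5.6.1 links the delay after such events to stable replacement of other hormones, so its relevance is plausible.
- **That Exclusions 05 and 06 and Inclusion 05 must be added too.** Unremitted acromegaly would be expected to fail listed Inclusions 02 and 03, and surgery or irradiation within 12 months falls under Exclusion 07, whether for acromegaly or for Cushing's disease. Adding Inclusion 05 fits awkwardly with the replacement-dose changes that Protocol 9.9.2.1 permits during the trial.

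**Conclusion.** The point holds as a low-cost improvement. As written, a subject who breaches only Exclusion 01 or Inclusion 08, or who follows a weight-reducing program or diet on study, stays in Sensitivity Analysis 1.

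The number of such subjects is unknown and likely small. The illustrated range of 0.04 to 0.50 points rests on an assumed net excess of one to four subjects and assumed shifts of 3 to 10 points. Entry violations bias the difference only through chance imbalance; equal numbers with equal shifts cancel.

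A reader might infer that the primary result is at risk. The documents do not support that: the ITT estimate, alpha, sample size and power do not depend on SAP 10.4.

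**What to change.** Make two changes in SAP 10.4 before unblinding, in line with the SAP's own commitment on timing:

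1. In the third bullet, change the list to: inclusion 02, 03, 04, 08 or exclusion 01, 07, 15, 18.
2. In the prohibited-therapy bullets, add: weight-reducing programs or diets (unless indicated for diabetes treatment). The exception matches Protocol 9.9.2.2.

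A sentence saying why other body-composition criteria, such as Exclusions 14 and 21, are left off would settle where the line is drawn.

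The cost is a few more subjects out of the Per-Protocol set and a slightly wider interval. If an assumed arm of 70 fell to 67, the 95% half-width, 1.96 × 3.7 × √(2/n), would rise from 1.226 to 1.253, a factor of √(70/67) = 1.022, or about 2%. The primary analysis is unchanged.

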4. LIST OF ABBREVIATIONS

µg	Microgram
ACP-001	TransCon PEG80 hGH
ACP-011	TransCon PEG40 hGH, Lonapegsomatropin
ACTH	adrenocorticotrophic hormone
ADA	anti-drug antibodies
AE	adverse event
AGHD	adult growth hormone deficiency
ALT	alanine aminotransferase
ANCOVA	analysis of covariance
AST	aspartate aminotransferase
AUC	area under the curve
AUEC	area under the effect curve
BMI	body mass index
CFR	Code of Federal Regulations
C _{max}	maximum observed concentration
CRO	Contract Research Organization
CT	Computed Tomography
d	Day
DCC	dual chamber cartridge
DPP-4	dipeptidyl peptidase-4
DXA	dual-energy x-ray absorptiometry
eCRF	electronic case report form
EDC	electronic data capture
eGFR	estimated glomerular filtration rate
E _{max}	maximum observed effect
EOT	end of trial
[REDACTED]	
FDA	Food and Drug Administration
fT3	free triiodothyronine
fT4	free thyroxine
GCP	Good Clinical Practice
GH	growth hormone
GHD	growth hormone deficiency
GHRH	growth hormone-releasing hormone

GHRP-2	growth hormone-releasing peptide 2
GLP	Good Laboratory Practice
GLP-1	glucagon-like peptide 1
GMP	Good Manufacturing Practice
hCG	human chorionic gonadotropin
HbA1c	hemoglobin A1c
HDL	high-density lipoprotein
hGH	human growth hormone
HIV	Human immunodeficiency virus
HREC	Human Research Ethics Committee
IB	Investigator's Brochure
ICH	International Council on Harmonization
ICF	informed consent form
IEC	Independent Ethics Committee
IFU	Instructions for Use
IGF-1	insulin-like growth factor-1
IGFBP-3	insulin-like growth factor binding protein-3
IMP	Investigational Medicinal Product
IND	investigational new drug
IP	investigational product
IRB	Institutional Review Board
IRT	interactive response technology
IUD	intrauterine device
kDa	Kilodalton
kg	Kilogram
LDH	lactate dehydrogenase
LDL	low-density lipoprotein
Lp(a)	lipoprotein(a)
MCH	mean corpuscular hemoglobin
MCHC	mean corpuscular hemoglobin concentration
MCV	mean corpuscular volume
MD	Doctor of Medicine
MDRD	Modification of Diet in Renal Disease
MedDRA	Medical Dictionary for Regulatory Activities
mg	Milligram
MHRA	Medicines and Healthcare products Regulatory Agency

mL	Milliliter
mPEG	methoxypolyethylene glycol
MRI	Magnetic Resonance Imaging
ng	Nanogram
NYHA	New York Heart Association
PD	Pharmacodynamics
PEG	polyethylene glycol

pH	power of hydrogen
PK	Pharmacokinetics

SAE	serious adverse event
SAP	Statistical Analysis Plan
SC	Subcutaneous
SD	standard deviation
SDS	standard deviation score
SE	standard error
SGLT-2	sodium-glucose cotransporter-2
SIV	site initiation visit
SOP	standard operating procedures
SUSAR	suspected unexpected serious adverse reaction
sWFI	sterile water for injection
TBI	traumatic brain injury

TSH	thyroid stimulating hormone
VLDL	very low-density lipoprotein
WHO	World Health Organization

5. INTRODUCTION

5.1. ADULT GROWTH HORMONE DEFICIENCY

Growth hormone (GH; somatotropin) is a product of endocrine secretion of the pituitary gland and targets many tissues to control metabolism in adults via its direct and indirect (via IGF-1) effects. In adipose tissue, GH is lipolytic and protects against hypoglycemia, and opposes the effects of IGF-1 (lipogenesis and reduced blood sugar). Growth hormone also has direct effects and indirect effects on bone metabolism, including on osteoblast proliferation and bone mineral density/bone accumulation (Olney 2003). New research continues to reveal other potential roles of GH, including regulation of cardiac and immune function, mental agility, and aging.

Adult growth hormone deficiency (AGHD) results from insufficient GH secretion from the anterior pituitary gland and may represent either a continuation of childhood-onset GHD or GHD acquired during adulthood. The primary etiology for adult-onset GHD is damage to the hypothalamic-pituitary region from tumors or treatment with surgery and radiation (Yuen 2019). Severe GHD has also been reported following treatment for acromegaly (Ronchi 2009) or Cushing's disease (Hughes 1999).

Clinically, AGHD is associated with central adiposity, diminished lean muscle mass, decreased bone mass, and reduced quality of life (Melmed 2019). Additional clinical features of untreated GHD include dyslipidemia, insulin resistance, and hepatic steatosis, which predispose this patient population to metabolic syndrome (Attanasio 2010) and significantly increase their cardiovascular morbidity and mortality (Gazzaruso 2014).

[figure not shown]
GH replacement therapy represents standard of care treatment that addresses multiple aspects of the condition (Ho 2007, Molitch 2011, Japan Endocrine Society 2019, Yuen 2019, Kim 2020). In particular, the lipolytic and anabolic actions of GH have been shown to confer beneficial effects on body composition across multiple trials (Møller 2009, Newman 2015). GH has also demonstrated important effects on bone mineral density (Snyder 2007) in longer term studies. Finally, quality of life improvements have been noted by patients' partners following initiation of GH therapy (Burman 1995).

Compliance with daily somatropin products in adults with GHD has been reported to be suboptimal. Based on survey data for 158 adults with GHD, the rate of non-compliance with GH therapy has been estimated to be 65% (Rosenfeld 2008).

